TITLE:

**Feasibility of an Immersive Virtual Reality Intervention for First Trimester Abortion:
A Pilot Study**

[name], MPH, FACOG¹, [name], BS¹

¹Obstetrics and Gynecology Department at the University of California, Los Angeles (UCLA)

ABSTRACT:

Perception of pain during surgical abortion is nuanced and affected by physical as well as psychosocial factors—notably the experience of anxiety—which can significantly increase perceived pain during abortion. It is found that women who suffer from anxiety are more likely to experience greater pain during gynecological procedures. Furthermore, pain management in the setting of gynecologic procedures is complex. While local anesthesia is commonly used, studies suggest that multimodal approaches may be more effective methods of pain management during gynecological procedures. However, the application of non-pharmacological pain and anxiety control adjuncts during gynecological procedures is not well studied, especially with regards to first-trimester surgical abortion. Recent innovation in virtual reality (VR) has generated increased interest in its potential use as an innovative and non-invasive method for managing patient anxiety and subsequently decreasing acute pain. Our work will assess the practicality and qualitative experiences of women using VR during first-trimester surgical abortion at the University of California Los Angeles West-Medical Obstetrics and Gynecology Clinic. Through this mixed method pilot study, we will evaluate the feasibility of using VR and its effect on procedure-related anxiety in the setting of first-trimester surgical abortion. Our work ultimately seeks to improve the experience of women undergoing first-trimester surgical abortion.

BACKGROUND:

a) Rationale:

Perception of pain and anxiety in first trimester surgical abortion

Most women experience moderate to severe pain during first-trimester surgical abortion despite various analgesic techniques.^{1,2} It is well-known that physiologic factors such as young maternal age, nulliparity, and a history of dysmenorrhea are associated with higher pain scores during first-trimester abortion. In addition, psychosocial factors play a large role in perception of pain during the procedure. These non-physiologic factors may include pre-procedural anxiety, fear, a sense of stigmatization or isolation, and self-assessed low pain tolerance. Of all these psychosocial factors, pre-procedural anxiety has the highest correlation with increased perception of pain during the surgical procedure.^{3,4,5} Accordingly, it has been found that pain management during gynecologic procedures is complex.⁶ While local anesthesia is commonly used, studies suggest that multimodal approaches, such as visual or auditory distraction, oral medication, and emotional support may be more effective methods of pain management during gynecological procedures.⁷

Virtual Reality

Figure 1. Example of Virtual Reality Headset

Virtual reality (VR) is a three-dimensional experience created by a headset fitted with a video display. The device, designed to be worn on the face, immerses the viewer in a virtual world and can create a visual and auditory distraction from the patient's present situation (*Figure 1*). VR devices are easily portable, intuitive to use, and non-invasive. Recent innovation in VR has generated increased interest in its potential use as a non-pharmacological adjunct for managing patient anxiety and subsequently decreasing acute pain.

Previous Studies and Scientific Significance

Studies have shown that VR is effective in reducing anxiety among a range of patients in differing circumstances, from patients undergoing dental procedures to patients undergoing chemotherapy.^{8,9} A recent randomized controlled trial has found that pre-operative VR can significantly reduce anxiety and increase patient satisfaction among patients undergoing craniotomy and spinal surgery.¹⁰ A study evaluating the feasibility of using VR among hospitalized patients revealed that most patients had positive experiences with VR and felt that it was not only capable of reducing anxiety but also pain.¹¹ Specifically, in the field of obstetrics and gynecology, a study showed that women undergoing episiotomy repair report markedly lower levels of anxiety after using VR as a form of adjunct pain therapy when compared to those who have not.¹² To our knowledge, the application of VR to first-trimester abortion has not been studied, and it is worthy of further research.

b) Objectives and Specific Aims:

1. *Assess the feasibility of using VR during first trimester surgical abortion under local anesthesia:*

Our work will assess the practicality and qualitative experience of women using VR during first trimester surgical abortion under local anesthesia. Semi-structured interviews will be conducted to understand the patient's experience of using VR.

2. Understand the effect of VR on procedure-related anxiety during first trimester surgical abortion:

We will analyze the anxiety scores of women before and after surgical abortion with the use of VR. In order to obtain an effect size for future studies, we will enroll a control group of patients receiving standard care and compare the anxiety scores between the two groups. The mean and standard deviation of anxiety scores for each group will be used to calculate power for future studies.

RESEARCH METHODS AND DESIGN

i) Trial Design/Sample Size:

We will conduct a mixed method pilot study to assess the feasibility of VR and understand its potential to decrease anxiety in the setting of first-trimester surgical abortion.

Specific aim 1: We will enroll a convenient sample of 15 participants who will use VR during first trimester surgical termination under local anesthesia in our clinic. Anxiety scores will be recorded before and after the procedure using a visual-analog scale. After the conclusion of the procedure, we will conduct semi-structured interviews to understand their overall experience with the VR device and software. We will ask patients to describe their experience in their own words and without prompting. This will then be followed by scripted probes regarding specific experiences with the VR use during the procedure and its effect on anxiety and pain. The interviews will be audio-recorded for analysis. We believe that this sample size will allow us to obtain thematic saturation to analyze patients' experiences.

Specific aim 2: After enrollment of the experimental group, we will enroll 15 patients receiving standard care in our clinic to compare the anxiety scores before and after the procedure. The enrollment of thirty patients will serve as a convenient sample in order to obtain an effect size. This data will help power further studies to determine the significance of VR on anxiety management.

ii) Participants:

We will screen patients over 18 years of age presenting to our obstetrics and gynecology clinic for first-trimester surgical abortion. Eligible patients must be English-speaking women seeking elective first trimester surgical abortion under local anesthesia. Patients will be excluded from the study arm if they have a history of motion sickness or vertigo, seizures or epilepsy, recent eye surgery, visual impairment, or claustrophobia. We will also exclude patients diagnosed or treated for anxiety in the past.

iii) Study setting:

The study will take place at the UCLA West-Medical Obstetrics and Gynecology clinic, which in the past year (from 1/1/2016 to 12/31/2016), has helped women receive a total of 160 first-trimester surgical abortions under local anesthesia. Due to the high volume of potential patients, we expect ease of enrollment.

iv) Virtual Reality:

We will use a commercially available VR device, comprised of a phone, headset and headphones. The phone is inserted into the headset to act as the visual display that can create different three dimensional environments. The device will require a wireless internet connection to work effectively. The patient will choose the virtual reality experience she prefers. More information about VR can be found at: appliedvr.zendesk.com

v) Outcome measurements:

We will collect standard demographic information (age, pregnancy history, ethnicity, race, educational and income level) from all participants using standard cross sectional survey. For each patient who has used the VR experience during the procedure, a pilot period measurement tool (Appendix A) will be administered after the recovery period. We will conduct a qualitative semi-structured interview in a private room (Appendix B). Audio-recordings of the patient's experience will be collected.

Anxiety scores: To assess the effect of VR on managing anxiety, we will measure the patient's perceived anxiety through survey scoring. Preoperatively, two surveys will be administered—a modified Amsterdam Preoperative Anxiety and Information Scale (modified APAIS) (Appendix C) and a visual analog scale for anxiety (numerical score with 0=minimum score 10 =maximum score) (Appendix D). The visual analog scale will again be used after the procedure.

vi) Statistical analysis:

In our qualitative analysis, interviews will be recorded and transcribed verbatim, and analyzed for thematic content using the Dedoose online software platform. Two members of the research team will code each transcript independently, with discrepancies resolved by consensus. For the quantitative component, the VAS scores, descriptive analysis using means and proportions for each variable of interest will be performed. Patterns of missing data will be assessed and imputation methods will be considered if appropriate. We will use mean and standard deviations for each group to detect the effect size for future studies.

IMPACT STATEMENT

Despite various analgesic techniques, first trimester surgical abortion is associated with significant pain, and the perception of pain, especially during abortion, is nuanced and affected not only

by physical but also by psychosocial factors.¹³ It has been shown that women present increased symptoms of anxiety, depressiveness, and stress before abortion, and that these symptoms can be significantly exacerbated by the perceived stigma of abortion.¹⁴ Because VR has been successful in decreasing anxiety and increasing patient satisfaction in various patient cohorts, it is worth exploring its possible use in first-trimester surgical abortion. The application of VR to the field of gynecological procedures has been limited, and to our knowledge, VR has never been offered to women seeking first-trimester surgical abortion. Our project will be the first to evaluate the feasibility of VR use during first-trimester surgical abortion. If feasibility is established, this pilot data will help us perform adequately powered future studies.

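### Both groups are convenience samples with no rule for whom to approach and no record of women passed over; approaching every eligible woman in order, with a log, would be a cheap improvement

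*Combined protocol and SAP*

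**What the plan says.** Under Research Methods and Design, i) Trial Design/Sample Size, Specific aim 1 says "We will enroll a convenient sample of 15 participants who will use VR". Specific aim 2 extends the description to both groups: "The enrollment of thirty patients will serve as a convenient sample in order to obtain an effect size". The groups are recruited one after the other: "After enrollment of the experimental group, we will enroll 15 patients receiving standard care in our clinic".

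Section ii) Participants adds a screening statement, "We will screen patients over 18 years of age presenting to our obstetrics and gynecology clinic for first-trimester surgical abortion". It does not say in what order eligible women are approached, who decides, or whether women who decline or are never approached are counted. The same section words some exclusions for one arm only: "Patients will be excluded from the study arm if they have a history of motion sickness or vertigo".

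Section iii) Study setting reports "a total of 160 first-trimester surgical abortions under local anesthesia" in 2016 and concludes: "Due to the high volume of potential patients, we expect ease of enrollment".

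The use of the Aim 2 result is given under Objectives and Specific Aims: "The mean and standard deviation of anxiety scores for each group will be used to calculate power for future studies". Section vi) Statistical analysis repeats that use. It plans a descriptive analysis, with no stated adjustment for baseline score or for selection.

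**The concern.** Under a convenience sample, someone on the clinic side can decide, woman by woman, whether to make the approach. This is a separate matter from who accepts once asked and from the order in which the two groups are filled. It would operate even if every woman approached agreed.

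Two results are exposed.

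- **Feasibility (Aim 1).** If women are passed over because the clinic is busy, the case looks difficult or the wireless connection is down, those omissions are themselves information about practicality. Without a log they are lost, and there is no denominator of eligible women. The fifteen interviews then describe only the women who happened to be chosen.
- **Effect size (Aim 2).** How anxious a woman appears is close to the outcome, which is an anxiety score. If that appearance influences who is approached, and does so differently in the VR and standard-care phases, the group means and SDs will differ partly for reasons unrelated to VR. A later trial sized on them could be too small or too large.

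**Working it through.** **The plan's own figure.** 15 + 15 = 30, which adds up. No alpha, power, SD or target effect is given, so there is no power calculation to reproduce.

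**Inputs from the documents.** 15 per group; convenience sampling for both groups; 160 procedures in a year.

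**Assumed inputs (not in the documents).** Fraction of eligible women approached, f = 0.5; correlation r = 0.2 to 0.5 between the trait guiding selection and the anxiety score; true standardised difference d = 0.5; share of procedures yielding an eligible, consenting woman, 30% to 50%.

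**1. Shift in one group's mean.** With a normal trait and selection of the top or bottom fraction f, the shift in SD units is r × φ(z)/f, where φ is the standard normal density and z the cut-off. At f = 0.5, φ(0)/0.5 = 0.798.

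| r | Shift in mean (SD) |
|---|---|
| 0.2 | 0.16 |
| 0.3 | 0.24 |
| 0.5 | 0.40 |

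The sign depends on whether calmer or more anxious women are favoured. The SD changes little. Its multiplier is √(1 − 0.798² × r²), which is 0.99 at r = 0.2 and 0.92 at r = 0.5.

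**2. What the comparison sees.** The shift in the difference is the VR shift minus the control shift. With the same f, r and direction in both groups it is zero. With r = 0.5 in one group and 0.2 in the other, same direction, it is 0.40 − 0.16 = 0.24 SD. The full 0.16 to 0.40 SD requires selection in one group and none in the other. If selection moves the before and after scores equally, it also cancels in the change score.

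**3. Consequence for a later trial** (two-sided 5%, 80% power; n per arm = 2 × (1.96 + 0.84)²/d²), with the full shift in one group:

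| Situation | d | n per arm |
|---|---|---|
| No selection | 0.50 | 63 |
| Shift favouring VR, 0.16 SD | 0.66 | 37 |
| Shift favouring VR, 0.40 SD | 0.90 | 20 |
| Shift against VR, 0.16 SD | 0.34 | 136 |

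**4. Random error, for scale.** SE(d) = √(2/15 + d²/60). The 95% half-width is 1.96 × SE: 0.72 at d = 0, 0.73 at d = 0.5 and 0.74 at d = 0.8. This exceeds every shift in step 1.

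**5. Time needed.** 160/52 = 3.1 procedures a week.

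- At 50%: 15/(160 × 0.5) × 52 = 9.75 weeks per group, so 19.5 weeks for both in sequence.
- At 30%: 15/(160 × 0.3) × 52 = 16.25 weeks per group, so 32.5 weeks for both.
- If study days covered only 40% of volume (a further assumption): 19.5/0.4 = 49 weeks to 32.5/0.4 = 81 weeks.

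**The case against.** A reader might infer that staff will give the headset to calm women while controls are taken as they come. The documents do not support that. They do not say who decides or on what basis. Controls are also a convenience sample, and they too must complete anxiety scores around an awake procedure, so the same discretion applies to them. Because VR is presented as a way of managing anxiety, staff might just as well favour visibly anxious women. The wording could even describe a size set by availability rather than any picking. All of this stands, and it is why the shift is stated without a direction. What survives is that discretion is neither limited nor recorded, and that identical selection in two separate phases, only one involving a headset, cannot be assumed.

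Anxiety is also measured before the procedure, on a visual analogue scale and a modified APAIS. Selection on calmness would show at baseline and might largely cancel in change scores. This is fair, but the plan does not say whether the effect size rests on after-procedure or change scores.

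With 15 per group, random error is larger than the illustrated shift. That is correct. However, the confidence interval describes random error only; it gives no sign that selection has occurred.

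Finally, Aim 1 has no numeric feasibility criterion, and its sample is justified by thematic saturation, so there is no pass mark to shift. The exposure there is to whose experience is reported. The study is also openly a pilot, but feasibility and an effect size are its declared products.

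**Conclusion.** The point holds as a worthwhile, inexpensive improvement, not as a flaw that invalidates the study. The sampling method is stated for both groups, and no rule or record constrains who is approached. Selection can affect the feasibility account and can bias the inputs to later power calculations, in a direction the documents do not settle.

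The 0.16 to 0.40 SD figure is an illustration. It rests on half of eligible women being approached in one group only, on a correlation of 0.2 to 0.5, and on an effect size taken from a single score. It is an upper reading for the group difference if the two groups are selected in the same direction or change scores are used.

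It would also be too strong to say that consecutive approach makes the Aim 2 comparison sound. Enrolment is sequential and not randomised, some exclusions apply to the VR arm only, and the groups are small. Those limits would remain.

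**What to change.** In i) Trial Design/Sample Size, replace the convenience-sample wording in both specific aims with text such as: *Every eligible woman attending on study clinic days fixed in advance will be approached in order of presentation, by the same rule for the VR group and for the standard-care group, until 15 are enrolled in each. A log will record the number eligible, approached, declining and not approached, with the reason for each woman not approached.*

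The sample size is unchanged. The cost is the protocol text, one log line per eligible woman and possibly slower enrolment. Under the 30% to 50% assumption both groups together take about 20 to 33 weeks using every procedure, and longer if study days cover only part of the volume, so the days should be chosen with that in mind. On the same days and at a given consent rate, approaching every eligible woman takes no longer than approaching some of them. The documents do not state staffing or the number of headsets, so the low cost is a judgement; the expected ease of enrolment supports it.

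### All 15 standard-care controls are enrolled after the 15 VR patients, without randomisation, so enrolment period cannot be separated from group in the Aim 2 effect size

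*Combined protocol and SAP*

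**What the plan says.** The protocol enrols a convenience sample of 15 VR patients first. The controls follow: "After enrollment of the experimental group, we will enroll 15 patients receiving standard care in our clinic to compare the anxiety scores" (Trial Design/Sample Size, Specific aim 2). That sentence goes on to say that the scores are those taken both before and after the procedure.

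The purpose of the control group is set out in Objectives and Specific Aims, aim 2: "we will enroll a control group of patients receiving standard care and compare the anxiety scores between the two groups", and then "The mean and standard deviation of anxiety scores for each group will be used to calculate power for future studies". Statistical analysis repeats it: "We will use mean and standard deviations for each group to detect the effect size for future studies". The Impact Statement relies on it again: "If feasibility is established, this pilot data will help us perform adequately powered future studies".

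Outcome measurements has modified APAIS and VAS taken before the procedure, and adds: "The visual analog scale will again be used after the procedure". Statistical analysis plans descriptive summaries only. It names neither the post-procedure VAS nor the change as the score behind the effect size, and it plans no adjustment for baseline or period. Randomisation is mentioned only for a cited outside trial.

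On eligibility, Participants says "Patients will be excluded from the study arm if they have a history of motion sickness or vertigo" and goes on to list seizures or epilepsy, eye conditions and claustrophobia. The next exclusion has no such limit: "We will also exclude patients diagnosed or treated for anxiety in the past".

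**The concern.** With all VR patients first and all controls second, anything that differs between the two periods also differs between the two groups. That could be staff, practice, the mix of patients, or who agrees to take part. The observed difference in mean anxiety is then the VR effect plus the period effect, and the data cannot split the two.

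This matters because the controls have one stated use, an effect size for sizing later studies. A confidence interval shows sampling error but not period bias, so a later team would have no sign that the figure needed correcting.

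A separate, conditional question is the study arm wording in Participants. If it means the VR group, the two groups are also drawn under different eligibility rules. If it means the whole study, they are not.

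**Working it through.** **Reproducing the plan's figure.** 15 + 15 = 30, the total stated in Specific aim 2. The protocol gives no alpha, power, SD or effect size, so there is no power calculation to reproduce.

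**Aliasing.** Code group as 1 for VR and 0 for control, and period as 0 for the first 15 enrolments and 1 for the last 15. In the stated order the group-period correlation is -1.00, and the matrix [intercept, group, period] has rank 2 of 3. The two effects cannot both be estimated. With the same 30 patients in alternating 1:1 order, the rank is 3, the correlation is -0.07 and the variance inflation is 1/(1 - 0.067²) = 1.004.

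A straight-line trend in enrolment order could be fitted to the stated design. Its correlation with group is -0.87, so the variance inflation is about 4.0. It also rests on a linearity assumption that cannot be tested, and it is not planned.

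**Length of the periods.** Study setting gives 160 procedures a year, or 160/12 = 13.3 a month. With uptake f assumed between 25% and 100%, a block of 15 takes 15/(13.3 × f) months: 4.5 at 25% and 1.1 at 100%. The exclusions make the 100% end unlikely.

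**Size of a possible bias.** The documents give no drift figure, so every drift size and correlation here is an assumption. Let the VAS drift linearly by D raw SDs from patient 1 to patient 30. The mean enrolment positions are 8 and 23, so the difference in group means is (23 - 8)/29 × D = 0.517 × D. For D = 0.2, 0.4 and 0.6 this is 0.10, 0.21 and 0.31 raw SD, sign unknown.

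*Drift equal in pre and post VAS, D = 0.6, pre-post correlation ρ:*
- post score: 0.31 raw SD
- change score: 0
- baseline-adjusted post VAS: 0.31 × (1 - ρ) = 0.22, 0.16, 0.09 raw SD for ρ = 0.3, 0.5, 0.7

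*Drift in post VAS only, D = 0.6.* The raw bias is 0.31 SD for all three scores. To put it in units of d, divide by each score's own SD: 1 for the post score, √(2(1 - ρ)) for the change, √(1 - ρ²) for baseline-adjusted post VAS. The standard error of d is √(2/15) = 0.365, and coverage of a nominal 95% interval by the normal approximation is Φ(1.96 - d/0.365) - Φ(-1.96 - d/0.365).

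| Score | ρ = 0.3 | ρ = 0.5 | ρ = 0.7 |
|---|---|---|---|
| Post: bias in d (coverage) | 0.31 (86%) | 0.31 (86%) | 0.31 (86%) |
| Change: bias in d (coverage) | 0.26 (89%) | 0.31 (86%) | 0.40 (80%) |
| Baseline-adjusted: bias in d (coverage) | 0.33 (86%) | 0.36 (83%) | 0.43 (78%) |

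**Sampling error for comparison.** 1.96 × 0.365 = 0.72 in d, larger than every bias in the table.

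**Consequence for a later trial.** Take a true d of 0.5 (assumed), a two-sided t-test at 0.05 and 80% power: 64 per arm are needed. Sizing on 0.7 (bias +0.2) gives 34 per arm and a true power of 53%. Sizing on 0.3 (bias -0.2) gives 176 per arm.

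**Eligibility, only if study arm means the VR group.** If a share p of controls came from the excluded groups and their VAS differed by δ SD (both assumed), the control mean shifts by pδ and the SD is multiplied by √(1 + p(1 - p)δ²). For p = 0.1, δ = 0.5: 0.05 SD and 1.01. For p = 0.3, δ = 1.0: 0.30 SD and 1.10.

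**The case against.** The strongest reply is that Specific aim 2 speaks of scores before and after the procedure, which points towards a pre-to-post comparison. A drift common to both measurements then cancels, and the 0.31 for the post score under common drift does not arise. This stands as far as it goes. But no section says that the change is the score behind the effect size, and a period or selection effect on the post score or on the change itself would not cancel.

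Second, the size is assumed throughout. No section supports a drift of 0.6 SD in one clinic over a few months. This also stands: only the aliasing is established from the text.

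Third, this is an openly labelled pilot with a convenience sample, a descriptive analysis and no hypothesis test, and sampling error exceeds any bias illustrated. That limits the severity. It does not remove the point, because the interval shows the sampling error and does not show the bias, and the protocol does not state the enrolment order as a limitation.

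A reader might go further and infer that the effect size will be wrong by 0.3 SD or so, that the groups certainly differ in eligibility, or that the pilot as a whole is compromised. The documents support none of these. They give no drift, the study arm wording has two readings, and the feasibility and interview work does not use the controls.

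**Conclusion.** The point holds for the Aim 2 between-group comparison. The stated enrolment order makes period and group inseparable, and the protocol takes that comparison into future power calculations with no named score, no adjustment and no stated limitation. The aliasing rests on the text alone. The biases do not: 0.26 to 0.43 in d, with 95% coverage of 89% down to 78%, assume a linear drift of 0.6 SD in the post score only and ρ from 0.3 to 0.7. The true effect could be nil, smaller, larger or of either sign. This is an avoidable bias in one aim of a small pilot. It should be fixed, and Aim 1 can proceed as planned. The study arm wording is a separate query to be settled and adds no weight of its own.

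**What to change.** Keep 30 patients.

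- Clarify what study arm means, and apply one eligibility list to both groups, including willingness to use VR.
- Enrol both groups over the same period, with 1:1 random allocation after baseline VAS and modified APAIS. Sealed opaque envelopes would do. Three permuted blocks of 4 and three of 6 in random order give 15:15 (12 + 18 = 30).
- Name baseline-adjusted post-procedure VAS as the score behind the effect size, and report it with its 95% confidence interval. Do not power later studies on the point estimate alone.

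The cost is a protocol and consent amendment and an allocation list, with no extra patients or assessments. The 15 VR interviews are kept but are spread over a longer period. Some patients may decline randomisation, and unblinded controls who hoped for VR may be disappointed, which could affect their anxiety scores. The documents give no staffing information, so the effect on staff time is unknown.

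If randomisation is not adopted, enrol concurrently under the same criteria and do not present the mean difference as a VR effect. If the sequential order is kept, state it as a limitation, apply the same restriction to the mean difference, and use the SDs for planning only if one eligibility list was applied.

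### Five VR-related exclusions are written for the study arm only, so the two groups that give the effect size for later studies have different eligibility rules

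*Combined protocol and SAP*

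**What the plan says.** Section ii) Participants first gives entry criteria that name no group: age over 18, presentation at the study clinic, and "Eligible patients must be English-speaking women seeking elective first trimester surgical abortion under local anesthesia". It then turns to exclusions: "Patients will be excluded from the study arm if they have a history of motion sickness or vertigo, seizures or epilepsy, recent eye surgery", with visual impairment and claustrophobia completing the list. The next sentence reads "We will also exclude patients diagnosed or treated for anxiety in the past" and names no arm.

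The two groups are defined in i) Trial Design/Sample Size. Aim 1 covers the VR group: "We will enroll a convenient sample of 15 participants who will use VR during first trimester surgical termination under local anesthesia in our clinic". For Aim 2, "After enrollment of the experimental group, we will enroll 15 patients receiving standard care in our clinic to compare the anxiety scores". Their purpose is given there too: "The enrollment of thirty patients will serve as a convenient sample in order to obtain an effect size".

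Aim 2, in b) Objectives and Specific Aims, says that "we will enroll a control group of patients receiving standard care and compare the anxiety scores between the two groups". Section vi) Statistical analysis adds: "We will use mean and standard deviations for each group to detect the effect size for future studies". No section describes matching, adjustment, or restriction of controls to women who could have used VR. The baseline data listed in v) Outcome measurements (age, pregnancy history, ethnicity, race, education, income) do not include the five conditions.

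**The concern.** The five conditions concern use of a headset, so it is understandable that they were written with the VR group in mind. However, the standard-care group exists to be compared with the VR group. If women with these conditions can enter only one side, the contrast mixes any effect of VR with the effect of who was allowed in. Claustrophobia is the item most plausibly tied to procedural anxiety.

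What is at stake is the main quantitative product of Aim 2, the effect size meant to power later work. A later randomized trial of VR would have to apply VR exclusions before allocation, and so to both arms. The control mean and SD from this pilot would then describe a population that the later trial does not enrol. Because the conditions are not among the data to be collected, VR-eligible controls could not be picked out afterwards.

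**Working it through.** **Stated figure.** 15 VR + 15 standard care = 30, which agrees with the plan. The plan contains no power calculation to reproduce.

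**Which criteria differ.**

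| Criterion | VR group | Standard care |
|---|---|---|
| Age, language, procedure, local anesthesia, clinic | applies | applies |
| Past anxiety diagnosis or treatment | applies | most naturally applies (no arm named, but the sentence begins with *also* straight after a study-arm list) |
| Five VR-related conditions | applies | no text applies them |

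The difference is therefore confined to the five conditions.

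**Size of the possible shift.** Let *p* be the share of controls with a barred condition, and *g* the mean difference between those women and the other controls on whatever contrast is used. The control mean moves by *p* × *g*. Neither quantity is in the documents. I assume *p* from 5% to 30%, *g* from -2 to +2 points on the 0–10 scale, and an SD of 2.5.

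| *p* | Expected affected controls, 15*p* | Chance of at least one, 1 − (1 − *p*)^15 | Shift at *g* = ±1, points (SD) | Shift at *g* = ±2, points (SD) |
|---|---|---|---|---|
| 5% | 0.75 | 0.54 | ±0.05 (0.02) | ±0.10 (0.04) |
| 10% | 1.5 | 0.79 | ±0.10 (0.04) | ±0.20 (0.08) |
| 20% | 3.0 | 0.96 | ±0.20 (0.08) | ±0.40 (0.16) |
| 30% | 4.5 | 0.995 | ±0.30 (0.12) | ±0.60 (0.24) |

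The direction is open because the plan does not fix whether the contrast is the post-procedure score or the before-to-after change. On post-procedure scores, more anxious controls would flatter VR. On change scores a constant excess cancels, and a larger fall among affected controls would count against VR.

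**Against sampling error.** The SE of the standardized difference with 15 per group is about √(2/15) = 0.365. With t(28, 0.975) = 2.048, the 95% half-width is 2.048 × 0.365 = 0.75 SD. The extreme shift is 0.24/0.365 = 0.66 SE.

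**What a modest shift would do to a later trial.** Take *p* = 20% and a difference of 0.5 SD, so a shift of 0.20 × 0.5 = 0.10 SD, and suppose the true effect is 0.50 SD (assumed). With n per arm = 2(1.960 + 0.842)²/d² (two-sided 5%, 80% power):

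- d = 0.50 gives 63 per arm.
- d = 0.60 (shifted up) gives 44 per arm, with about 65% actual power.
- d = 0.40 (shifted down) gives 99 per arm.

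**The case against.** The strongest case for leaving this as a minor clarification has four parts.

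1. **The term is undefined.** *Study arm* could be loose wording for the whole study. That is possible, but the plan separates an experimental group from a control group, and the listed items concern VR use, so the VR-only reading is the natural one. If the broader meaning was intended, the same edit simply makes it explicit.
2. **The plan has partial safeguards.** Anxiety is scored before and after the procedure, and the wording of Aim 2 leans toward that comparison. A baseline imbalance would be visible, and a constant one would cancel on change scores. The anxiety-history exclusion, if it covers both groups, removes the controls most likely to make *g* large. These points stand and limit the likely size. They do not deal with a different response to the procedure, and the contrast is still not fixed.
3. **The extreme of the range is unlikely.** *g* averages over all five conditions, and only claustrophobia has an obvious link to anxiety. Pairing 30% with 2 points is a limit, not an expectation. At 10% and 1 point the shift is 0.04 SD, about 0.11 SE. The chance of at least one affected control shows that such women are likely to be present, not that the result is biased.
4. **Larger problems remain.** Sampling error at 15 per group is bigger, and controls are a later, non-randomized convenience sample. Both are true. Neither is a reason to keep a second difference that wording alone can remove.

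**Conclusion.** The concern holds: as written, the two groups compared in Aim 2 are drawn under different eligibility rules, and nothing in the plan repairs this. Confidence is high on the wording. The consequence is modest and uncertain: under the assumptions above the shift could be negligible, and zero is inside the range. Unlike sampling error, though, it is not expressed by a confidence interval and would not shrink if more patients were enrolled under the same rule. It should be fixed because the remedy costs little and the effect size is what Aim 2 is meant to deliver. The feasibility and interview work of Aim 1 is not affected.

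**What to change.** In ii) Participants, replace the two exclusion sentences with one statement covering both groups, for example:

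> The following exclude a woman from both the VR group and the standard-care group: claustrophobia; visual impairment; recent eye surgery; epilepsy or seizures; a history of vertigo or motion sickness; any past diagnosis of, or treatment for, anxiety. One checklist is used at screening for both groups.

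This also settles the ambiguity over the anxiety-history criterion. If controls have already been enrolled, record the five conditions for them and report the effect size in VR-eligible controls alongside the one in all controls.

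**Cost.** N stays 30 and the VR-group exclusions do not change. The control population becomes slightly narrower. At *p* = 5% to 30%, 15/0.95 = 15.8 to 15/0.70 = 21.4 otherwise eligible women would be needed to yield 15 controls. The 160 procedures a year cited in iii) Study setting become 160 × 0.95 = 152 to 160 × 0.70 = 112, before other criteria and consent; 15 controls are 10% to 13% of these.

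**Limit.** The change does not cure the non-comparability that comes from enrolling controls after the VR group without randomization. That needs to be addressed separately.
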